# 7.1.6.2 Day 4: Allowance + 1 Day

- Collection of stool specimens (the following items will be tested by the microbiological laboratory)
  - Bacterial culture test
- Confirmation of IMP compliance
- Confirmation of patients' clinical symptoms on Days 1 to 3 (daily stool count, stool symptoms, bloody stool, fever, abdominal pain, nausea, and vomiting)
- Assessment of clinical response
- Clinical laboratory tests (hematology test, biochemistry test, and urinalysis)
- Blood sampling for measuring plasma concentration
  - Inpatient: 1 (± 15 minutes), 2 (± 15 minutes), and 4 hours (± 30 minutes) after morning administration
  - Outpatient: once within 12 hours after morning administration but before evening administration.
- 12-lead ECG
- Vital signs (blood pressure, pulse rate, and body temperature)
- Physical examination
- Confirmation of adverse events
- Confirmation of concomitant drugs and therapies

# 7.1.6.3 Day 8 (End of Treatment): Allowance + 1 Day

- Collection of stool specimens (the following items will be tested by the microbiological laboratory)
  - Bacterial culture test
  - Drug sensitivity test on isolated strains
- Confirmation of IMP compliance
- Confirmation of patients' clinical symptoms on Days 4 to 7 (daily stool count, stool symptoms, bloody stool, fever, abdominal pain, nausea, and vomiting)
- Assessment of clinical response
- Clinical laboratory tests (hematology test, biochemistry test, and urinalysis)
- 12-lead ECG
- Vital signs (blood pressure, pulse rate, and body temperature)
- Physical examination
- Confirmation of adverse events
- Confirmation of concomitant drugs and therapies

# 7.1.6.4 Day 14 (at Follow-up 1): Allowance ± 3 Days

- Confirmation of patients' clinical symptoms on Days 8 to 13 (daily stool count, stool symptoms, bloody stool, fever, abdominal pain, nausea, and vomiting)
- Clinical laboratory tests (hematology test, biochemistry test, and urinalysis)
- Vital signs (blood pressure, pulse rate, and body temperature)
- Physical examination
- Confirmation of adverse events
- Confirmation of concomitant drugs and therapies

# 7.1.7 Time of Withdrawal and Withdrawal Examination: Allowance ± 2 Days

The investigator or subinvestigator will perform the following examination, observation, and assessments for patients who withdrew from the trial within 2 days after the day when withdrawal is considered necessary. If the patient refuses to undergo any examinations at the time of withdrawal, or if the investigator or subinvestigator judges that any examinations at the time of withdrawal cannot be performed due to an emergency or other circumstances (eg, SAE or recurrence of CDI), of the examination items specified for the time of withdrawal, only those items that can be performed will be performed. Results of tests and assessment, the date of measurements and assessment,

and the date of blood/urine/stool sampling will be recorded in the source records and CRF.

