# **Definitions of Terms**

Term	Definition
Screen failure	A screen failure is a patient from whom written informed consent was obtained, but to whom the investigational medicinal product was not assigned.
Trial start date for individual patient	The day of obtaining the patient's written informed consent
Trial completion date for individual patient	CDI group: The completion day of follow-up 2 (FU2) or withdrawal examination for individual patients Enteric infection group: The completion day of follow-up 1 (FU1) or withdrawal examination for individual patients
Trial withdrawal date for individual patient	The day when withdrawal is considered necessary by the investigator or subinvestigator for individual patient or the day of withdrawal examination
Trial period for individual patient	Period from the day of obtaining the patient's informed consent to the day of trial completion. It does not include the follow-up period after the trial completion date for individual patient.

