#### 1) Pharmacokinetics:

Following single administrations of OPS-2071 at doses of 30, 60, 120, 240, 300, 600, 900, and 1200 mg in a fasting state, median  $t_{max}$  was 1.0 to 4.0 hours postdose. Following multiple dose administration at doses of 60, 120, 300, and 600 mg after a light meal, median  $t_{max}$  was 2.0 to 3.5 hours in the Singapore trial, and following multiple dose administration before meals, median  $t_{max}$  was 2.5 to 3.5 hours in the Korean trial. OPS-2071  $C_{max}$ , AUC from time zero to the last quantifiable concentration (AUC0-t) and AUC from time zero extrapolated to infinity (AUC0-\infty) values increased dose-dependently but in a less than dose proportional manner following single- and multiple-dose administration. The mean apparent terminal phase half-life ( $t_{1/2}$ ) of OPS-2071 was variable at 10 to 21 hours for the single dose treatments across the 30 to 1200 mg dose in the Singapore trial and approximately at 12 to 50 hours in the Korean and Japanese trials across the same dose range.

Following administration of OPS-2071 at a single dose of 600 mg after consumption of a meal,  $C_{max}$  was 2.21,  $AUC_{0-t}$  and  $AUC_{0-\infty}$  were 2.04-fold higher compared with the values following administration in a fasted state. In multiple dosing of OPS-2071, steady-state conditions were achieved by Day 2 of administration of OPS-2071.

The mean percent of OPS-2071 excreted in urine ( $fe_{u,72h}$ ) was approximately 2.4% or less of the administered dose following single and multiple dose administration. The mean amount excreted in the feces as a percentage of dose administered ( $fe_{f,72h}$ ) ranged from approximately 30.0% to 55.0% of the administered dose following single dose administration.

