# 8.4 Follow-up Investigation of Adverse Events

The term "recovered" used below means that a patient who had an AE prior to the start of IMP administration returned to his or her original condition, or a patient who had an AE

after the start of IMP administration returned to his or her condition before the start of IMP administration.

- 1) If an AE has not resolved by the day of trial completion or the day of withdrawal, the investigator or subinvestigator will explain to the patient the need for follow-up investigation after the end of the trial and will request the patient's cooperation. The investigator or subinvestigator will conduct a follow-up investigation within 4 weeks after the end of the trial and record information regarding the AE in the source documents. If an AE is not resolved by the day of trial completion or the day of withdrawal, the investigator or subinvestigator will record the outcome in CRF as "recovering/resolving," "not recovered/not resolved," or as otherwise appropriate.
- 2) If an AE has not resolved by the day of the follow-up investigation and a causal relationship with the IMP cannot be ruled out, follow-up investigation will be continued until the event resolves or becomes stable and information regarding the AE will be recorded in the patient's source documents. If a causal relationship between the AE and the IMP can be ruled out, no further follow-up will be made beyond the day of the initial follow-up investigation.
- 3) If, between the day of trial completion or day of withdrawal and the day of the follow-up investigation, a new SAE for which a causal relationship with the IMP cannot be ruled out occurs, or if an AE is not resolved by the day of trial completion or the day of withdrawal and for which a causal relationship with the IMP cannot be ruled out becomes serious, follow-up investigation will be conducted until the AE resolves or becomes stable, and information regarding the AE will be recorded in the source documents.
- 4) If a serious AE for which a relationship with the IMP cannot be ruled out is discovered after the day of trial completion or the day of withdrawal, or after the day of the initial follow-up investigation (if performed), follow-up investigation will be conducted until the AE resolves or becomes stable or until follow-up of the patient becomes impossible and information regarding the AE will be recorded in the source documents.

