#### 9.2 Criteria and Procedures for Withdrawal of Individual Patients

In any of the events listed below, the investigator or subinvestigator will discontinue IMP administration, perform the tests to be performed at withdrawal stipulated in Section 7.1, Schedule and Procedures of the Trial, and promptly inform the sponsor of the withdrawal (Annex, Emergency Contact). The investigator or subinvestigator will record the date and reason for withdrawal in the source documents and CRF.

If withdrawal is necessitated by problems with safety, such as the occurrence of an AE or aggravation of the underlying disease, the investigator or subinvestigator will promptly take appropriate measures and perform follow-up if necessary (refer to Section 8.4 Follow-up Investigation of Adverse Events).

- 1. If the patient wishes to withdraw
- 2. If it is found after the start of the trial that the patient did not meet all the inclusion criteria or fell under any of the exclusion criteria
- 3. If a drug or therapy from either item 1 or item 7 in the list of prohibited concomitant drugs and therapies is used or judged to be required
- 4. If an AE making continuation of trial participation difficult occurs
- 5. If the female patient is found to be pregnant
- 6. If symptoms of the primary disease exacerbate, and the investigator or subinvestigator judges that it is not appropriate to continue the trial participation
- 7. If it becomes impossible to comply with the protocol for any another reason or if the investigator or subinvestigator judges that it is necessary to discontinue the trial participation for any another reason

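### Patients who stop the drug leave safety observation within about 2 days, so adverse event incidence by dose rests on unequal observation windows

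*Protocol*

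**What the plan says.** **Stopping and leaving are coupled.** For any of seven listed reasons, Section 9.2 says that "the investigator or subinvestigator will discontinue IMP administration, perform the tests to be performed at withdrawal stipulated in Section 7.1". One of the reasons is "If an AE making continuation of trial participation difficult occurs". No general route is described for staying under observation while off the drug.

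**The examination closes the patient's trial.** Section 7.1.7 applies it "for patients who withdrew from the trial within 2 days after the day when withdrawal is considered necessary". The Definitions of Terms give the CDI completion date as "The completion day of follow-up 2 (FU2) or withdrawal examination for individual patients"; the enteric definition is parallel, with FU1. Of the individual trial period they add: "It does not include the follow-up period after the trial completion date for individual patient".

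**Afterwards.** Under Section 8.4, for an event unresolved at completion or withdrawal, the investigator "will conduct a follow-up investigation within 4 weeks after the end of the trial and record information regarding the AE in the source documents"; the CRF holds the outcome as it stood on the last trial day. New events in that period are pursued only if serious and possibly related. Sections 8.2.2(1) and (2) send those to the sponsor, in principle within 24 hours.

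**Analysis.** Section 11.3.1 tabulates numbers of patients with events, and incidence, by disease group and dose. Section 10.4 lists CRFs among the data the sponsor collects; it does not list the Section 8.4 follow-up records.

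**The concern.** Safety is part of the first primary objective, and each disease-by-dose cell has about 10 patients. Incidence is compared across doses as a simple proportion. If one dose has more early stops, its patients are watched for less time after dosing, and events starting later have less chance of being counted. A better tolerated dose, with more completers, is watched for longer. The comparison then partly reflects observation time rather than tolerability. Adjustment in an analysis plan could account for the time observed, but it cannot recover events that were never collected.

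**Working it through.** **1. The protocol's own figure.** Section 3.2, item 4, places FU2 28 days after the end of treatment. Day 38 − Day 10 (last dose) = 28 days, which reproduces it.

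**2. Observation after the last dose.**

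| | Completers | With the ±3 day visit allowance | Early stoppers |
|---|---|---|---|
| Enteric | 14 − 7 = 7 days | 4 to 10 days | about 2 days |
| CDI | 38 − 10 = 28 days | 25 to 31 days | about 2 days |

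**3. Share of the schedule seen.** A patient who stops on Day 4 is seen to about Day 6: 6/14 = 43% (enteric) or 6/38 = 16% (CDI).

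**4. What is and is not captured after withdrawal.**

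| Event | Route | Can be missed from the tables? |
|---|---|---|
| Event that caused the stop | CRF | No |
| Event open at withdrawal | CRF, with outcome at that day | Event no; later course yes |
| New serious event, possibly related | Expedited report (8.2.2); source documents (8.4) | Known to the sponsor; no CRF route stated |
| New serious event, judged unrelated | None stated | Yes |
| New non-serious event | None stated | Yes |

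**5. Illustration under stated assumptions.** Take one further type of event, unconnected with the reason for stopping, with constant hazard and an assumed risk p = 30% over the full schedule. The probability of seeing it is 1 − (1 − p)^(days observed / days in schedule). For a Day 4 stop:

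- CDI now: 1 − 0.7^(6/38) = 5.5%. With the completers' 28 days after dosing: 1 − 0.7^(32/38) = 25.9%.
- Enteric now: 1 − 0.7^(6/14) = 14.2%. With the completers' 7 days: 1 − 0.7^(11/14) = 24.4%.

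Expected incidence in a cell of 10 with k such stoppers is [(10 − k) × 30% + k × probability seen] / 10:

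| | k | Present rule | Equal post-dose window | Difference (points) |
|---|---|---|---|---|
| CDI | 1 | 27.5% | 29.6% | 2.0 |
| CDI | 3 | 22.6% | 28.8% | 6.1 |
| Enteric | 1 | 28.4% | 29.4% | 1.0 |
| Enteric | 3 | 25.3% | 28.3% | 3.1 |

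Differences were taken before rounding. The risk, the stop day and the number of stoppers are all assumptions.

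**6. Statements that do not agree.** The heading of 7.1.7 allows ±2 days for the withdrawal examination; its text says within 2 days after the decision, and Table 7-1 says +2. Section 8.5.3 foresees the protocol's follow-up observation after a pregnant patient stops the drug, whereas 9.2 and the Definitions of Terms end the trial period at the withdrawal examination.

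**The case against.** The strongest reply is that most of what matters is already captured. A patient stopped for an adverse event is in the numerator of both the any-event row and the row for events leading to withdrawal, and lost visits cannot remove that patient. Open events are followed: Section 7.1.9 requires additional examinations, and Section 8.4 requires follow-up within 4 weeks, continued to resolution or stability if possibly related. Section 11.3.1 sets no end date for the events it tabulates. The Data Review Committee judges safety during the treatment period, so lost follow-up visits do not enter its dose decisions. Early stoppers also have less exposure, so part of any lower incidence may be real. All of this stands and limits the point; none of it provides a route for new non-serious or unrelated serious events.

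Three stronger readings are tempting and are not supported:

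- **That later findings go only to source documents.** Possibly related serious events are reported to the sponsor.
- **That the source-document rule itself biases the dose comparison.** Section 8.4 applies it to completers and withdrawn patients alike; only the length of the window differs.
- **That residual drug makes 2 days too short.** A reader might take the half-lives of "approximately at 12 to 50 hours in the Korean and Japanese trials across the same dose range" and compute 0.5^(48/50) = 51% remaining at 48 hours. The same section gives 10 to 21 hours for the Singapore trial; these are single-dose terminal values, and it reports steady state by Day 2. A governing 50-hour half-life would have reached only about 49% of steady state at 48 hours. The argument is unreliable and unnecessary.

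**Conclusion.** The point holds as a matter of data capture. The Section 11.3.1 incidence by dose rests on about 2 days of observation after stopping for early stoppers, against 7 (enteric) or 28 (CDI) for completers. The possible under-count is confined to new non-serious events and unrelated serious events starting after withdrawal, together with the later course of open events.

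Its true size cannot be derived, because the protocol gives neither an event hazard nor a dropout rate. The illustrative loss of 1 to 6 percentage points for a single further event type rests on a constant hazard, a 30% risk, and Day 4 stops unrelated to that event. It does not apply to the any-event row for patients who stopped because of an event. A reader might infer that toxicity is broadly under-counted in those who stop for it; the documents do not support that, since the causative event is counted. This is a worthwhile, inexpensive improvement rather than a flaw that invalidates the safety analysis.

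**What to change.** The change concerns data collection only and leaves untouched when or why the drug is stopped.

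1. For patients who stop the drug and do not withdraw consent, collect adverse events, laboratory tests and vital signs at the scheduled FU1 (and FU2 in CDI). After a Day 4 stop, Day 14 and Day 38 lie 10 and 34 days later, which covers the completers' 7 and 28 days and allows a common cut-off.
2. In Section 8.4, record the follow-up outcome of open events, and any possibly related serious event found in follow-up, in the CRF, and include them in the Section 11.3.1 tables.
3. Reconcile the withdrawal window across the heading and text of 7.1.7 and Table 7-1, and reconcile Section 8.5.3 with Section 9.2.

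The cost is amendment wording, some CRF fields, and one or two already defined visits for the few early stoppers. Some will decline, so the windows will become closer rather than equal.

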## 7.1.7.1 Clostridium Difficile Infection Group

- Collection of stool specimens (the following items will be tested by the microbiological laboratory)
  - Bacterial culture test
  - Toxin A/B assay
- Confirmation of IMP compliance until withdrawal
- Confirmation of patients' clinical symptoms until withdrawal (daily stool count, stool symptoms, bloody stool, fever, abdominal pain, nausea, and vomiting)
- Assessment of clinical response: to be performed only in case of withdrawal during the IMP administration period
- Assessment of recurrence of CDI: to be performed only in case of withdrawal after completing the IMP administration
- Clinical laboratory tests (hematology test, biochemistry test, and urinalysis)
- 12-lead ECG: to be performed only in case of withdrawal during the IMP administration period
- Vital signs (blood pressure, pulse rate, and body temperature)
- Physical examination
- Confirmation of adverse events
- Confirmation of concomitant drugs and therapies

## 7.1.7.2 Enteric Infection Group

- Collection of stool specimens (the following items will be tested by the microbiological laboratory)
  - Bacterial culture test: to be performed only in case of withdrawal during the IMP administration period
- Confirmation of IMP compliance until withdrawal
- Confirmation of patients' clinical symptoms until withdrawal (daily stool count, stool symptoms, bloody stool, fever, abdominal pain, nausea, and vomiting)
- Assessment of clinical response: to be performed only in case of withdrawal during the IMP administration period
- Clinical laboratory tests (hematology test, biochemistry test, and urinalysis)
- 12-lead ECG: to be performed only in case of withdrawal during the IMP administration period
- Vital signs (blood pressure, pulse rate, and body temperature)
- Physical examination

Protocol No. 341-13-002

- Confirmation of adverse events
- Confirmation of concomitant drugs and therapies

## 7.1.8 Information at Conclusion (Discontinuation) of the Trial

The investigator or subinvestigator will register the necessary items in IVRS or IWRS at the time of conclusion (discontinuation) of the trial for each patient.

## 7.1.9 Follow-up Investigation

If an AE has not resolved by FU1, FU2, or withdrawal, additional examinations of the AE will be performed in accordance with Section 8.4, Follow-up Investigation of Adverse Events.

#### 7.2 Method of Evaluation

# 7.2.1 Safety Evaluation

## 7.2.1.1 Height, Body Weight

Measure height and body weight according to the procedures stipulated by the trial site, and record the date of measurements and results in the source documents and CRF.

## 7.2.1.2 Physical Examination

The investigator or subinvestigator will examine the patients, record the physical findings in source documents, and evaluate any clinically significant events as AEs, and record the AEs in CRF. In case if abnormal findings are not judged as AEs, enter the reason in source documents.

# 7.2.1.3 Clinical Laboratory Tests (Hematology Test, Biochemistry Test, and Urinalysis)

At screening, the following clinical laboratory test items will be measured at each trial site according to the procedures stipulated by each trial site. Record the date and result of examination in source documents, not in CRF.

The sample collected at the screening examination will be dispensed in two containers and tested by the trial site and central laboratory.

The central laboratory will determine the following clinical laboratory test items at all the prescheduled time points (including screening examination). Use the container provided by the central laboratory when sampling. The investigator or subinvestigator will record the sampling date in the source documents and CRF, and review the report on clinical

Protocol No. 341-13-002

laboratory tests performed by the central laboratory, date, and sign the report. In case if abnormal values are not judged as AEs, enter the reason in source documents.

Follow the separately stipulated procedures for collection, handling, storage, and shipment method of specimens.

Table 7.2-1 Clinical Laboratory Test Items

Hematology test	Hemoglobin (Hb), hematocrit (Hct), red blood cell count (RBC), white blood cell count (WBC), differential leukocyte count (neutrophils, eosinophils,			
	basophils, monocytes, lymphocytes), platelets (PLT), mean corpuscular			
	volume (MCV), mean corpuscular hemoglobin (MCH), mean			
	corpuscular hemoglobin concentration (MCHC)			
Biochemistry test	Aspartate aminotransferase (AST), alkaline phosphatase (ALP), alanine			
	aminotransferase (ALT), total protein (TP), albumin (ALB), total bilirubin			
	(T-BIL), uric acid (UA), urea nitrogen (UN), creatinine (Cr), serum glucose			
	(GLU), triglyceride (TG), cholesterol (TC), $\gamma$ -glutamyltransferase ( $\gamma$ -GTP),			
	Na, K, Cl, Ca, C-reactive protein (CRP)			
Urinalysis	pH, protein, glucose, ketone, bilirubin, urobilinogen, blood, nitrite,			
-	leucocytes, and specific gravity			

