#### Singapore trial (Trial 341-12-001)

Following a single administration of OPS-2071 or placebo in a fasting state, five of 20 subjects (25%) experienced seven treatment-emergent adverse events (TEAEs) (OPS-2071: seven events in five subjects). There were two TEAEs of Grade 4 severity [Common Terminology Criteria for Adverse Events (CTCAE) severity grading], reported for one subject (30 mg); these were events of syncope and hemorrhage intracranial, assessed by the investigator as not related to the investigational medicinal product (IMP), but considered to be SAEs necessitating withdrawal. Subjects also experienced upper respiratory tract infections (URTIs; 2/20 [10%]), cough (1/20 [5%]), rhinorrhea (1/20 [5%]) and atrial fibrillation (1/20 [5%]).

Following administration of OPS-2071 at 600 mg in both fed and fasted states, one subject (1/12 [8.33%]) experienced two TEAEs, which were mild gastroenteritis and URTI.

Following multiple administration of OPS-2071 in a fed state, nine subjects (9/32 [28.13%]) experienced 15 TEAEs. Treatment-related TEAEs were five events of alanine aminotransferase (ALT) increased (5/32 [15.63%]), and one event (1/32 [3.13%]) each of ventricular extrasystoles, aspartate aminotransferase (AST) increased, electrocardiogram QT prolonged (described in the CRF as "QTcB > 450 ms"; however, central measurements revealed that QTcB and QTcF were < 450 ms), gamma-glutamyltransferase increased and headache.

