#### Korean trial (Trial 341-KOA-1301i)

Following a single administration of OPS-2071 or placebo in a fasting state, 10 of 64 subjects (15.6%) experienced 14 TEAEs (OPS-2071: 12 events in eight subjects; placebo: two events in two subjects). TEAEs reported were two events (2/64 [3.1%]) each of URTI and epistaxis, and one event (1/64 [1.6%]) each of vision blurred, abdominal pain, abdominal pain upper, diarrhoea, oral pustule, dizziness, headache, pleuritic pain, rhinorrhoea, and dry skin.

Following multiple administration of OPS-2071 or placebo before morning meal and before evening meal, 10 of 32 subjects (31.3%) experienced 22 TEAEs (OPS-2071: 18 events in seven subjects; placebo: four events in three subjects). TEAEs reported were three events (3/32 [9.4%]) of diarrhoea, two events (2/32 [6.3%]) each of headache and somnolence, and one event (1/32 [3.1%]) each of dry eye, visual acuity reduced, abdominal distension, abdominal pain, abdominal pain upper, nausea, sensation of foreign body, epistaxis, oropharyngeal pain, pharyngeal haemorrhage, pleuritic pain, dry skin, pruritus, rash, and rash erythematous.

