#### Japanese trial (Trial 341-13-001)

After single oral administration of OPS-2071 or placebo in a fasting state, a total of 25 TEAEs were reported for 22 (34.38%) of the 64 subjects (OPS-2071: 18 events in 16 subjects; placebo: seven events in six subjects). The highest incidence of TEAEs occurred in the System Organ Class of gastrointestinal disorders (13 events in 11 of the 64 subjects [17.19%], comprising 11 events of diarrhoea (10/64 [15.63%]) and two events of abdominal pain (1/64 [1.56%]). The other TEAEs comprised three events of headache (3/64 [4.69%]), two events (2/64 [3.13%]) each of pharyngitis and blood creatine phosphokinase increased, two events (1/64 [1.56%]) of ALT increased, and one event (1/64 [1.56%]) each of subcutaneous hematoma, AST increased, blood bilirubin increased, back pain, and proteinuria.

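### Creatine phosphokinase is the only laboratory adverse event named from phase 1 that has no matching test in Table 7.2-1

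*Protocol*

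**What the plan says.** Section 1.2.2 of the protocol summarises three phase 1 trials in healthy volunteers. Laboratory adverse events appear in two of them.

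- **Singapore, multiple dose:** "nine subjects (9/32 [28.13%]) experienced 15 TEAEs". Those named as treatment-related include raised ALT (five events), AST and gamma-glutamyltransferase.
- **Japan, single dose, fasting, OPS-2071 and placebo pooled:** "two events (2/64 [3.13%]) each of pharyngitis and blood creatine phosphokinase increased", raised ALT, and one event each of "subcutaneous hematoma, AST increased, blood bilirubin increased, back pain, and proteinuria".
- **Korea:** neither the single-dose nor the multiple-dose list names a laboratory event.

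Table 7.2-1 fixes the panel that the central laboratory measures at every scheduled time point. The biochemistry row includes AST, ALT, total bilirubin and gamma-GTP and closes with "Na, K, Cl, Ca, C-reactive protein (CRP". The urinalysis row reads "pH, protein, glucose, ketone, bilirubin, urobilinogen, blood, nitrite", followed by leucocytes and specific gravity. CPK is in no row. No other section schedules a CPK test or says why it is left out.

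Safety is part of a primary objective (Section 2), laboratory tests are a safety endpoint (Section 3.3.1), and Section 1.2.3 describes this as the first trial in patients.

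**The concern.** A safety panel for a first trial in patients would normally cover the laboratory events already seen in volunteers. This one does so for every event the protocol names except CPK. The two CPK events followed one dose. Here patients take the drug twice daily for 7 or 10 days, that is 14 or 20 administrations.

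Under the panel as written, a reader of the final tables could take the absence of CPK findings as reassurance when it reflects only the absence of scheduled measurement. The DRC, which reviews safety before the next dose step, would have no scheduled CPK values either. The protocol's own causality rule (Section 8.3.4) treats an event seen in earlier clinical trials as a reason why a relationship cannot be ruled out. Earlier observations are thus held to matter, yet this one is not followed up.

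**Working it through.** **1. The plan's own figure.** 2/64 = 3.125%, which agrees with the stated 3.13%.

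**2. Named phase 1 laboratory events against Table 7.2-1.**

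| Event named in Section 1.2.2 | Trial | Item in Table 7.2-1 |
|---|---|---|
| ALT increased | Singapore, Japan | ALT |
| AST increased | Singapore, Japan | AST |
| Gamma-glutamyltransferase increased | Singapore | gamma-GTP |
| Blood bilirubin increased | Japan | T-BIL |
| Proteinuria | Japan | urine protein |
| Blood CPK increased | Japan | none |

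Five of the six are covered.

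**3. Are the event lists complete?**

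- Singapore, single dose: 2 + 2 + 1 + 1 + 1 = 7 (stated 7).
- Singapore, multiple dose: 5 + 5 = 10 named, of 15 stated, so five events are unnamed.
- Korea, single dose: 2 × 2 + 10 = 14 (stated 14).
- Korea, multiple dose: 3 + 2 × 2 + 15 = 22 (stated 22).
- Japan: 13 gastrointestinal + 3 headache + 2 pharyngitis + 2 CPK + 2 ALT + 5 single events = 27. The stated total is 25, which equals 18 on OPS-2071 plus 7 on placebo.

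The Japanese list, the source of the CPK count, therefore does not add up.

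**4. What scheduled measurement could show.** The documents give no CPK rate for OPS-2071 alone, so I assume p = 2/64. The exact (Clopper-Pearson) 95% interval for 2 of 64 is 0.4% to 10.8%. The chance of at least one case in n patients is 1 − (1 − p)^n.

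| n | Expected cases, n × 2/64 | Chance of at least one |
|---|---|---|
| 10 (one disease group at one dose) | 0.3 | 1 − (62/64)^10 = 27% |
| 20 (one dose group) | 0.6 | 1 − (62/64)^20 = 47% |
| 60 (whole trial) | 1.9 | 1 − (62/64)^60 = 85% |

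Over the interval, the figure for 60 patients runs from 1 − (1 − 0.0038)^60 = about 20% to 1 − (1 − 0.108)^60 = above 99%.

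If the discrepancy in step 3 affected the CPK count and only one event were real, p = 1/64 gives 60/64 = 0.9 expected cases and 1 − (63/64)^60 = 61%.

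**The case against.** The strongest case against is that the signal is too thin to justify a change.

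- The two events come from one single-dose trial, with no arm, severity or causality given. Both could have been in placebo subjects.
- Phase 1 also gave 7 days of twice-daily dosing at up to 1200 mg/day, three times the highest daily dose possible here (1200/400 = 3). The Korean multiple-dose list accounts for all its events ("10 of 32 subjects (31.3%) experienced 22 TEAEs") and has no CPK rise. The Singapore treatment-related list has none.
- The toxicology summary mentions no muscle finding.
- The panel covers the only laboratory events that the protocol calls treatment-related, and no passage contradicts another on this point.

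Most of this stands, and it sets the priority. It does not remove the gap. The protocol does not say whether CPK was measured in the multiple-dose trials, so their silence is not evidence of absence.

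Four stronger readings are tempting, and the documents support none of them.

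1. A reader might infer that a CPK rise cannot be detected at all. Section 8.1.1 counts any abnormal laboratory finding as a possible adverse event, and nothing forbids an unscheduled test. That route depends on someone ordering the test, so it would usually miss a symptom-free rise and gives no denominator.
2. A reader might infer that CPK is the only phase 1 laboratory event left uncovered. That is shown only for named events: five Singapore multiple-dose events are unnamed, and further detail is left to the investigator's brochure.
3. A reader might infer that OPS-2071 raises CPK. Nothing in the protocol attributes the events to the drug.
4. A reader might expect that measuring CPK would reveal a dose trend. With about 0.6 expected cases per 20-patient dose group and no placebo arm, it could not, nor could it separate drug from background.

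**Conclusion.** The point holds as a low-priority, cheap improvement. Among the laboratory events the protocol names from phase 1, CPK is the only one without a scheduled test. The trial as written will produce no CPK table and no scheduled CPK data for the DRC.

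The consequence is modest. The 85% and 47% figures assume that a rate pooled over drug and placebo after one dose carries over to repeated dosing in patients. They also rest on a count from a list that does not reconcile, and the interval around that rate is wide. Measuring CPK would give a description of how often rises occur, with no attribution to the drug and no dose-response. That is still more informative than an empty table that could be mistaken for a negative finding.

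**What to change.** Add CPK to the biochemistry row of Table 7.2-1 at the existing central-laboratory time points: screening, Day 4, end of treatment, FU1, FU2 (CDI group only) and withdrawal. Summarise it descriptively by disease group and dose with the other biochemistry under Section 11.3.1. If the sponsor prefers not to add it, state the reason in Section 7.2.1.3.

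Reconcile the Japanese event counts in Section 1.2.2 (27 itemised, 25 stated), and give the CPK events by arm if the data allow.

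The cost is one more analyte on biochemistry samples already scheduled, with no new visit or procedure. The downside is a few incidental high values to explain.
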